#### **4.4 Adverse Event Relationship to Study Drug**

For all adverse events grade  $\geq 3$  that occur after randomization, study investigator(s) will assess the potential relationship of the event to the study medication. One of the following designations will be used:

- i. Related: There is a reasonable possibility that the AE may be related to the study agent(s).
- ii. Not related: There is not a reasonable possibility that the AE may be related to the study agent(s). Alternative etiology, diagnosis or, explanation for the AE should be provided.

#### **4.5 Reporting Adverse Events**

The IRB (or Human Subjects Committee) for the site where the event occurred will receive immediate notification of all serious adverse events (SAE) that are ALSO deemed protocol related, OR for any unanticipated problem (UP; which are by definition protocol related). **NOTE:** *an adverse event (of any grade) that is unexpected, is reasonably believed to be related to study participation, and involves risk to the participant or others should be captured as a UP (per definition above 4.2).*

The site will enter this information into the adverse event log and SAE/UP case report form (via REDCap reporting). The data coordinating center (DCC) will distribute a summary of each SAE/UP event to the remaining clinical sites and participating institutions for submission to their respective IRBs.

The site will also complete FDA Form 3500 (MedWatch; see below), and submit this form to the FDA (via online reporting) and also to the DCC. Within 2 business days of learning of the event, clinical sites must:

- a) Inform local IRB per institutional guidelines and timelines

- b) fill out an SAE/UP case report form, via REDCap online reporting
- c) fill out an MedWatch Form FDA 3500
- d) either submit MedWatch Form FDA 3500 to the FDA or complete voluntary reporting online via FDA MedWatch (see below for link)
- e) email the completed MedWatch Form FDA 3500 to: study PI ([name]; [contact]), DCC ([name]; [[contact]](mailto:[contact]))

The DCC will submit FDA Form 3500 and any other information on the SAE/UP from the REDCap CRF, to a representative for Merck Pharmaceuticals. Reporting of all SAE/UP events will be made to FDA and Merck Pharmaceuticals using FDA Form 3500.

FDA MedWatch reporting forms may be found at:  
<http://www.fda.gov/safety/medwatch/howtoreport/downloadforms/default.htm>

FDA MedWatch voluntary reporting can be performed at:  
<https://www.accessdata.fda.gov/scripts/medwatch/>

## 4.6 Participant Withdrawal

Participants may withdraw from the study at any time at their request, as described in the consent. All randomized participants will be encouraged to complete a final study visit, including all visit procedures.

## 5 Data and Safety Monitoring Plan

The Principal Investigator (PI) will be responsible for ensuring participants' safety on a daily basis. A Data and Safety Monitoring Board (DSMB) will be formed with [name] as the un-blinded statistician; other members will not be from institutions involved in the study and will be approved by NIA. Committee members will have experience with HIV/AIDS clinical research studies. Prior to enrollment the DSMB will review the protocol and data analysis plan.

The DSMB will act in an advisory capacity to the NIA Director to monitor participant safety, evaluate the progress of the study, and review procedures for maintaining the confidentiality of data, the quality of data collection, management, and analyses. During the study the DSMB will meet at least yearly.

Refer to the DSMB Charter and data and safety monitoring plan for details.

### 5.1 Interim Analysis

Most of the primary blood and tissue outcomes will not be available until after visits are completed, as samples will be batch processed at our participating laboratory site. Hence, there will be no formal interim analyses for efficacy or futility related to the main study outcomes.

However, the lead study statistician will prepare and submit reports to the DSMB every 3 months documenting study enrollment totals and adverse events. While we do not anticipate significant issues with safety in this short-term study, a recommendation by the DSMB to stop the study would likely be based on an adverse event rate that is deemed unacceptably high.

Recommendations from the DSMB (e.g., continue the study as planned), and a letter summarizing the findings at the end of the study, will be transmitted to each site for submission to their IRB.

## **5.2 Frequency and Content of Data and Safety Monitoring**

To ensure compliance and data are reported correctly and completely, CRF data will be monitored monthly for completeness and compliance with the study protocol. Queries for clarification or data completion will be posted to a site-specific and password protected section of the LIFE-HIV website.

The PI will be informed of serious adverse events as soon as they occur and will notify the NIA and DSMB within 24 hours of notification. During the study the DSMB will meet at least yearly either in-person or by teleconference call to review study progress, data quality, and participant safety. An initial DSMB meeting will be scheduled as soon as any of the following occurs:

- i. Six months have elapsed since enrollment of the first patient
- ii. 50% of goal enrollment is achieved
- iii. 30 person-years of follow-up is achieved

The data and safety monitoring report will include data on: enrollment (including progress), visit attendance, completeness of data, completeness and quality of specimen collection, baseline characteristics, adherence and discontinuation of medication, and side effects and adverse events.

## **5.4 DSMB Conflict of Interest and Protection of Confidentiality**

DSMB members should have no direct involvement with the study investigators or intervention. Each DSMB member will sign a Conflict of Interest Statement which

includes current affiliations, if any, with pharmaceutical and biotechnology companies (e.g., stockholder, consultant), and any other relationship that could be perceived as a conflict of interest related to the study and / or associated with commercial interests pertinent to study objectives.

Data will be presented in a blinded manner during the open sessions of the DSMB. At DSMB meetings, data and discussion are confidential. Participant identities will not be known to the DSMB members.

## **5.5 DSMB Responsibilities**

The DSMB Charter provides a detailed list of the DSMB responsibilities. They include:

- Review the research protocol, informed consent documents and plans for data safety and monitoring;
- Recommend subject recruitment be initiated after receipt of a satisfactory protocol;
- Evaluate the progress of the trial, including periodic assessments of data quality and timeliness, recruitment, accrual and retention, participant risk versus benefit, performance of the trial sites, and other factors that can affect study outcome;
- Consider factors external to the study when relevant information becomes available, such as scientific or therapeutic developments that may have an impact on the safety of the participants or the ethics of the trial;
- Review study performance, make recommendations and assist in the resolution of problems reported by the Principal Investigator;
- Protect the safety of the study participants;
- Report to NIA on the safety and progress of the trial;
- Make recommendations to the NIA and the Principal Investigator concerning continuation, termination or other modifications of the trial based on the observed beneficial or adverse effects of the treatment under study;
- Ensure the confidentiality of the study data and the results of monitoring; and,
- Assist the NIA by commenting on any problems with study conduct, enrollment, sample size, and/or data collection.

## **6 ANALYSIS PLAN**

The general goal of this study is to evaluate the potential treatment effects of losartan for reducing systemic inflammation and improving immune recovery. For the effect of losartan on systemic inflammation, the outcome will be the average of log IL-6 levels (plasma) from samples obtained at months, 1, 3, 6, 9, and 12; two pre-treatment log IL-6 measurements will be averaged to estimate baseline log IL-6 level. The primary

analysis will be intention to treat using a linear model for the aforementioned outcomes with treatment group indicator as the main predictor, fitted using the Generalized Estimating Equations approach with an independence working correlation structure. The model will be adjusted for baseline log IL-6 and clinical center. The hypothesis of no treatment effect will be assessed by considering the statistical significance of the treatment group indicator. Additional analyses will consider change in IL-6 at specific visit time points, as well as the percent of participants that achieve an IL-6 level <1.1 pg/mL (i.e., the 25th percentile among HIV+ patients with viral suppression in the SMART/ESPRIT/SILCAAT trials)

Immune recovery will be assessed by modeling log10 CD4+ T-cell counts in blood, using a linear mixed effects model that, in addition to the model components described for the systemic inflammation analysis above, incorporates a main effect for time (in months), a treatment-by-time interaction, and individual-specific intercepts and slopes (for time). The hypothesis of no treatment effect on rate of yearly change in log10 CD4 counts will be evaluated by considering the statistical significance of the treatment-by-time interaction term.

Subgroup analyses will be performed to explore potential for differential treatment effects (e.g., entry CD4 count [including ≥ vs. < 350], CD4:CD8 ratio, use of statins, aspirin, or other drugs with potential anti-inflammatory or anti-fibrotic properties, and co-morbidities or polymorbidities). Trends in treatment effects on the primary outcome (log IL-6) over time will be assessed using linear mixed effects models similar to those described for the modeling of log10 CD4+.

The main analyses for primary and secondary outcomes will be intention to treat. As secondary analyses, we will perform per-protocol ('on treatment') and compliance-adjusted analyses, and will also carry out analyses using all available data by multiply imputing missing longitudinal outcome measurements via the chained equations method, using linear mixed effects models incorporating baseline covariates, the treatment indicator, and non-missing outcome measurements.

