### Randomization and Blinding

Eligible participants who consent to study procedures will be randomized 1:1 to receive losartan or matching placebo, with stratification by clinical site and by whether the participant consents to undergo a LN biopsy. Treatment assignments will be generated using a permuted block randomization scheme. Sites will use a secure, on-line program to obtain treatment assignments. The program will also verify eligibility and the existence of key baseline data. Treatment assignments will be verified and recorded in a dataset blinded to view by site staff.

A bottle ID number (BID) unique to each bottle will be assigned to participants, and used by study staff to obtain the correct blinded study drug. Sites will not have access to the treatment assignment linked to each bottle number, and bottle numbers will not be assigned in sequence.

Blinding will occur at 3 levels: 1) treatment assignment will be blinded, 2) interim data summaries will be blinded to all but the unblinded statistician and 3) core lab staff will be blinded to treatment group. In the rare event that the blind must be broken, every effort will be made to minimize the extent of the unblinding (for staff and participants) and an assessment of blinding will occur at the end of the study.

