## 2.6 Study Visit Schedule

Participants will be screened and, if eligibility criteria are met, will be randomized at the baseline visit to start active study drug or matched placebo (blinded). Randomization must occur within 90 days of all screening labs. *NOTE: the 90-day screening to randomization window applies to all participants, both those co-enrolled into the LN biopsy substudy and those not co-enrolled.*

Baseline laboratory evaluation must occur within 30 days of randomization. For participants enrolled in the LN biopsy substudy, baseline labs cannot be drawn within the 7 days following the biopsy procedure. A LN biopsy specimen must be obtained prior to randomizing the participant into the LN substudy. If a biopsy procedure is attempted but a LN specimen is not obtained at baseline, the participant will still be eligible to be randomized into the main study (but not the LN substudy). *NOTE: the biopsy procedure may occur after the baseline labs are obtained but still prior to randomization.*

After screening and baseline visits, participants will start losartan 50mg daily (or placebo) and return for a lab draw to assess toxicity (BMP only) at week 2. At the week 2 visit (after toxicity lab results return), participants will increase to losartan 100mg daily (or placebo) if they meet criteria based on results from the 2-week assessment (see section 2.4 above). Subsequent study visit procedures will occur in the context of visits at months 1, 3, 6, 9, and 12. For participants enrolled in the LN biopsy substudy, month 12 visit labs cannot be drawn within the 7 days following the month 12 biopsy procedure (*NOTE: the biopsy procedure may occur after the month 12 labs are obtained*). Participant should continue to take study medication until all study visits are completed; for participants enrolled in the LN biopsy substudy this includes BOTH the month 12 biopsy as well as the month 12 labs.

The target visit window for each study visit is guided by anticipated study drug quantity that the participant will have at the time. For week 2 and month 1, this corresponds to a 14-day target window (or +/- 7 days). Corresponding target windows for month 3, 6, 9, and 12 study visits are 32 days (or +/- 16 days).

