## 2.7 Sample Size Considerations

### Power for Reduced Inflammation (IL-6 levels)

- The primary analysis will compare baseline-adjusted log IL-6 measurements at 1, 3, 6, 9 and 12 months between treatment groups.
- Standard deviation (SD) data from SMART (n=122; baseline and month 1) and ESPRIT (n=147; baseline and month 12) on participants who were on continuous ART between both time points were used to estimate a log IL-6 SD of 0.74 pg/mL.
- We assumed a 28% reduction in IL-6 with losartan was plausible based on our pilot data and data from HIV negative studies in the general population.

Based on assumptions above, assuming 5% missing data, and considering the potential

clinical risk reduction associated with IL-6 changes of this magnitude (see epidemiologic data, following paragraph), a total sample size of n=110 will be enrolled. With this sample we will have 80% power to detect an absolute reduction of 0.3 log(IL-6), corresponding to a 26% reduction in IL-6, with a two-sided Type I error of 0.05.

Pooled data from 3,766 participants in SMART, ESPRIT and SILCAAT trials who were taking continuous ART with an HIV RNA level <400 copies/mL at entry—a group that resembles our target population—indicate that a 26% lower baseline IL-6 level is associated with a 34% lower risk of serious non-AIDS events or death from any cause.

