### **3.9 Lymphatic Tissue Assessment**

Lymph node (LN) biopsy will be performed in a subset of at least 30 participants at baseline and month 12. Criteria for enrollment into the LN substudy include: a) participant consent, b) lack of contraindications to the LN biopsy procedure, and c) palpable lymph nodes on exam by site investigator or research coordinator. All participants at NIH will be offered participation into the LN substudy, and participants at HCMC and Allina/Abbott Northwestern (in Minneapolis) will be offered participation until/if 25 patients are enrolled. Planned analyses will be exploratory in nature focused on assessment of: a) collagen deposition reflecting fibrosis in T-cell zone, b) changes in CD4 T-cell populations, c) changes in the structure of the FRCn, and d) changes in cellular immune activation in lymphatic tissue.

Biopsies will be performed at the University of Minnesota (for HCMC and Abbot Northwestern sites) and the NIH clinical center, by general surgeons using a research facility equipped with inpatient rooms. Tissue specimens are placed into fresh 4% paraformaldehyde for 24 hours and then transferred to 80% ethanol for paraffin embedding. LN tissue can also be divided at the bedside prior to processing to accommodate additional methods that requiring non-fixed tissue.

Changes in LN T-cell zone collagen, the size of T-cell populations, and the FRCn structure will be measured using established methods of IHC with antibody staining and quantitative image analysis (QIA) developed by [name] lab at the University of Minnesota. A similar approach will be used to assess cellular immune activation within lymphatic tissue.

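### The primary IL-6 model leaves out one of the two randomisation strata (LN-biopsy consent); add it with a small-sample-corrected robust standard error, or say why it is omitted.

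*Combined protocol and SAP*

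**What the plan says.** Section 2.4 (Randomization and Blinding) allocates participants 1:1, "with stratification by clinical site and by whether the participant consents to undergo a LN biopsy". It adds: "Treatment assignments will be generated using a permuted block randomization scheme". The block size is not given.

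Section 6 describes the primary IL-6 analysis as a linear model with a treatment indicator, "fitted using the Generalized Estimating Equations approach with an independence working correlation structure". On covariates it says only: "The model will be adjusted for baseline log IL-6 and clinical center". It names neither the variance estimator nor a small-sample correction. The CD4 mixed model takes over the same components, so it omits consent too.

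The only other mention of covariates is at the end of Section 6. It concerns unspecified baseline covariates in the secondary multiple-imputation analysis and does not restore the stratum to the primary model.

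Two other sections bear on the missing factor:

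- Section 3.9 ties the biopsy offer to site. It says "All participants at NIH will be offered participation into the LN substudy", and at two Minneapolis sites biopsy is offered up to a cap.
- Section 2.6 requires a specimen before randomisation into the LN substudy. A participant whose attempted biopsy yields none may still enter the main study, so consent and substudy membership can differ.

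**The concern.** Stratified blocks force the arms to balance on consent. If consent predicts the outcome, that balance removes its contribution from the true variance of the treatment estimate, whether or not the model contains the term. A model without the term leaves that contribution in the residuals, so a properly calibrated SE overstates the true variability. The test then runs below its nominal level and gives up some of the power that the stratification provided.

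The unnamed SE matters as well. With 110 participants an uncorrected sandwich SE is biased downward, which works in the opposite direction. Whether the primary test runs above or below 5% therefore depends on two choices, one made without explanation and one not made.

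**Working it through.** **Inputs from the documents.** Section 2.7: 110 participants, log IL-6 SD 0.74, difference 0.3, 5% missing, two-sided alpha 0.05, 80% power. (Section 2.1 gives 120 participants; 110 is used here.) Section 6: follow-up at months 1, 3, 6, 9 and 12. Section 3.9: at least 30 biopsy participants.

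**Assumptions not in the documents.** Four sites of 20/40/25/25 with 10/12/8/0 consenters; blocks of 4 within site × consent; consent explains R² = 0, 2, 5 or 10% of residual variance after baseline IL-6 and site.

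**Step 1: the plan's power.** With 55 × 0.95 = 52.25 per arm, SE = 0.74 × √(2/52.25) = 0.1448, z = 0.3/0.1448 = 2.072, and power = Φ(2.072 − 1.96) = 54.5%. The stated 80% does not follow from SD 0.74 alone. It needs a participant-mean residual SD of (0.3/2.802)/√(2/52.25) = 0.547. If 0.74 is the single-visit SD, this implies a within-person correlation of 0.43. The main results use 0.547, so that power is anchored to the stated 80%.

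**Step 2: closed form for omitting the term.** With balance within strata, the true SD shrinks by √(1 − R²), while a calibrated SE that ignores consent does not.

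- Ratio of SE to SD = 1/√(1 − R²) = 1.01, 1.03, 1.05 at 2, 5, 10%.
- Type I error = 2Φ(−1.96/√(1 − R²)) = 4.8, 4.4, 3.9%.
- Power forgone = Φ(z/√(1 − R²) − 1.96) − Φ((z − 1.96)/√(1 − R²)). With z = 2.802 this is 80.8 − 80.2, 82.0 − 80.6 and 84.0 − 81.3, or about 0.5, 1.4 and 2.7 points. With z = 2.072 (SD 0.74 used directly) it is 0.8, 2.0 and 4.2 points.

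**Step 3: simulation of the planned model.** Independence GEE with SEs clustered by participant and 5% of visits missing at random; 40,000 null runs and 40,000 runs at −0.3 per setting. Monte Carlo SE is about 0.11 points for type I error and 0.2 for power.

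| R² | 0% | 2% | 5% | 10% |
|---|---|---|---|---|
| True SD of estimate, without / with term | 0.1063 / 0.1063 | 0.1047 / 0.1046 | 0.1036 / 0.1035 | 0.1004 / 0.1002 |
| Type I %, HC2-type + t, without / with | 5.03 / 5.02 | 4.76 / 5.00 | 4.53 / 5.11 | 3.82 / 4.83 |
| Power %, HC2-type + t, without / with | 80.0 / 79.9 | 80.0 / 80.5 | 80.6 / 82.1 | 81.1 / 83.9 |
| Type I %, uncorrected + z, without / with | 6.00 / 6.12 | 5.72 / 6.07 | 5.43 / 6.20 | 4.59 / 5.93 |
| Power %, uncorrected + z, without | 82.1 | 82.1 | 82.9 | 83.1 |

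The true SD hardly changes when the term is added, so the issue is the reported SE. Without the term, the uncorrected SE divided by the true SD is 0.966, 0.981, 0.992 and 1.024, so an over-large SE shows only at 10%. With the term it is 0.961–0.968.

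**Step 4: sensitivity.** A second simulation (6,000 trials per setting, within-person correlation 0.5, consent effects of 0 to 1 SD beyond baseline IL-6) gave type I error of 6.1% falling to 2.2% for the planned model with an uncorrected SE. Adding consent uncorrected gave 5.9–6.4%, and adding it with a Mancl-DeRouen correction gave 4.1–4.7%. With eight sites and a 0.5 SD effect, those three analyses gave 5.8, 6.8 and 3.8%.

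**Step 5: how plausible is each R²?** The within-site variance of consent under the assumed layout is (20×0.25 + 40×0.21 + 25×0.2176)/110 = 0.1713. The implied gap between consenters and non-consenters at the same site and baseline is √(R² × 0.547²/0.1713) = 0.187, 0.296, 0.418 log units. Consenters' IL-6 would have to be 21, 34 or 52% higher, or 17, 26 or 34% lower.

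**The case against.** The mismatch is plain, but several arguments reduce its weight.

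- **Little is at stake.** There is no bias. In the credible range (R² near 2%) the term moves type I error from 4.76% to 5.00% and power by half a point. Nothing in the documents shows that consent is prognostic, and site absorbs part of any association. This stands, and it is why the point is minor.
- **The SE correction does most of the work.** HC2-type with t and no consent term already gives 5.03% and 4.76% at R² of 0 and 2%. This also stands: the correction is worth naming on its own. The dependence runs the other way, because adding the term without the correction leaves the test near 6%.
- **There is no clear power gain over the likely default.** Against the uncorrected test without the term, the full change moves power by 79.9 − 82.1 = −2.2, 80.5 − 82.1 = −1.6, 82.1 − 82.9 = −0.8 and 83.9 − 83.1 = +0.8 points at R² of 0, 2, 5 and 10%. The arithmetic stands, but at 0, 2 and 5% the default's extra power comes from running above 5%.
- **The magnitudes rest on assumed inputs.** Site layout, block size and R² are assumed, and the residual SD is back-solved. The figures are illustrative; the direction follows from the closed form.
- **The stratum is not fully defined.** A consenter with a failed biopsy might be entered in either stratum. The documents leave this open, so the value recorded at randomisation should be used.

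**Conclusion.** The concern holds as a minor point. It is certain that one of the two stratification factors is absent from the primary model without explanation and that the SE type is unnamed. The size of the effect is conditional. If consent explains 2–10% of residual variance, a corrected test without the term runs at 4.8–3.8% and forgoes about 0.5 to 83.9 − 81.1 = 2.8 points of power on the 80% anchor (0.8–4.2 points if SD 0.74 is used directly). The lower values are the more credible. If consent is not prognostic, nothing is lost by leaving it out. The planned analysis remains unbiased throughout, and no gain is claimed for the CD4 treatment-by-time test.

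**What to change.** Replace the covariate sentence in Section 6 with wording to this effect:

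> Covariates are baseline log IL-6, clinical center, and LN-biopsy consent stratum as recorded by the randomisation program. Inference uses a small-sample-corrected robust standard error (HC2-type, e.g. Kauermann-Carroll) with a t reference distribution on participants minus model parameters.

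Enter site and consent as main effects, since some site-by-consent cells may be sparse. Code every participant by the recorded stratum, including a consenter whose baseline biopsy yielded no specimen, and not by substudy membership. If the factor is omitted on purpose, give the reason and still name the SE type.

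The cost is one binary covariate already recorded, one degree of freedom and a wording change. If consent is irrelevant, the term costs about 0.1 power point (80.0 vs 79.9%). A Mancl-DeRouen correction is also safe but more conservative: type I error of 4.2–4.4% with the term, and 1.5–2.0 points less power than HC2-type (77.9, 78.6, 80.3, 82.4% against 79.9, 80.5, 82.1, 83.9%). The term should not be added with an uncorrected sandwich SE.
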